## **5.5 Withdrawal of Subjects**

Subjects may voluntarily withdraw from study participation at any time for any reason. Alternatively, subjects may be withdrawn at the Investigator's discretion if it is in the subject's best interest.

Every effort should be made for subjects who withdraw from the study, either voluntarily or at the Investigator's discretion, to undergo end of study assessments (Visit 8), if possible. If possible, the subject should also be advised to come for the two Safety Follow-up visits (Visit 9 and Visit 10) at 1 and 2 weeks after last dose. If a subject refuses end of study procedures, the reason for refusal should be fully documented in the subject's source document and recorded in the study specific electronic case report form (eCRF). It is the subject's right to withdraw from the study without providing a reason. In this case, the source documents and the eCRF should document the reason for withdrawal as "withdrawal of consent." Withdrawn subjects will not be replaced.

## **5.6 Discontinuation of Study Treatment**

Discontinuation of study treatment does not necessarily constitute withdrawal from the study.

If any subject is discontinued from study treatment, the reason for discontinuation will be documented in the eCRF. If the reason for discontinuing study treatment is an AE or an abnormal laboratory test result, the specific event or test will be recorded in the eCRF.

If possible, subjects who are permanently discontinued from study treatment before the Week 24 visit should undergo all study assessments up to and including the Week 24 (or Early Termination Visit – Visit 8) and Safety Follow-up visits where appropriate. All subjects that discontinue study treatment should attend at least 2 further assessments after the last dose of study drug.

Guidance on when study treatment must be discontinued is in [Section 7.4, Voclosporin Dose Modification](#).

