-------------	---

Procedures (cont'd)	
Doses and dose increments smaller than anticipated may be proposed for Cohort 2 based on the safety and tolerability results from the Cohort 1.
 
All subjects will complete dosing through 24 weeks of study treatment and will have 2 Safety Follow-Up visits, 1 and 2 weeks after completion of treatment (i.e., at Week 25 and Week 26). Subjects who permanently discontinue study treatment before the Week 24 visit will return for all remaining study visits and assessments, including the 2 Safety Follow-Up visits, unless they have withdrawn consent.

Sample Size:	
As this is an exploratory study, sample size calculations are not required. It is estimated that approximately 20 subjects will be recruited, with up to 10 subjects in Cohort 1 and at least 10 subjects in Cohort 2.

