## AUR-VCS-2017-03 SCHEDULE OF EVENTS

Visit	Visit 1 Screening Period		Visit 2 Baseline	Visit 3	Visits 4-5	Visit 6	Visit 7	Visit 8 End of Treatment/ Early Termination	Visit 9 Safety Follow-up	Visit 10 Safety Follow-up
Day/Week	Screening to Day -1		Day 1 (Within 1 Wk Post Qualifying Assessment)	Wk 2 (±3 Days)	Wks 4, 8 (±3 Days)	Wk 12 (±3 Days)	Wk 18 (±5 Days)	Wk 24 (±7 Days)	Wk 25 (±3 Days) or Premature Disc. +7 Days	Wk 26 (±3 Days) or Premature Disc. +14 Days
	Screening Visit 	Stability Assessments 1 & 2, Optional 3 & 4 								
Informed consent	✓									
Eligibility criteria	✓	✓								
Renal biopsy 								✓ 		
Medical history and demography	✓									
Physical exam 	✓		✓					✓		
Vital signs 	✓	✓	✓	✓	✓	✓	✓	✓	✓	✓
ECG 	✓		✓					✓		
Laboratory assessments 	✓	✓	✓	✓	✓	✓	✓	✓	✓	✓
Pharmacokinetics 					✓			✓		
Urinalysis and urine microscopy	✓		✓	✓	✓	✓	✓	✓	✓	✓
FMV urine collection 	✓	✓	✓	✓	✓	✓	✓	✓	✓	✓
24-hour urine 			✓			✓		✓		
QoL 			✓					✓	✓	✓
Pregnancy test 	✓	✓	✓	✓	✓	✓	✓	✓		
Adverse events	✓ 	✓	✓	✓	✓	✓	✓	✓	✓	✓
Concomitant medications	✓	✓	✓	✓	✓	✓	✓	✓	✓	✓
Dispense study medication/ compliance 			✓	✓	✓	✓	✓	✓ 		
First dose of study medication			✓ 							

- 1 Stability assessments to occur at 14-day intervals ( $\pm$  3 days) with first assessment approximately 2 weeks after the screening visit. Stability assessments 1 and 2 are mandatory; assessments 3 and 4 are optional if additional time is required for the subject's clinical status to stabilize. Note that the laboratory assessments and FMV results of the last stability assessment will be used as the qualifying values for eligibility. Enrollment of eligible subjects must occur within 1 week of the final stability assessment.
- 2 If a subject has not had a recent renal biopsy, one may be performed to assess eligibility for the study provided informed consent has been given. The biopsy must have been performed 6 months prior to the screening visit. Biopsy results over 6 months prior to screening may be permitted following review with the Medical Monitor to confirm eligibility. Repeat renal biopsies may be done at Week 24 in a subset of subjects at selected sites.
- 3 Complete physical exam at screening; abbreviated exam at all other visits.

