- 15 First dose of study medication should occur in the morning the day after dispensing.

Notes: Subjects who discontinue therapy will be requested to attend their regularly scheduled study visits to the end of the study.

AE = Adverse event; BID = Twice daily; BP = Blood pressure; Disc. = Discontinuation; ECG = Electrocardiogram; FMV = First morning void; Min = Minimum; QoL = Quality of life; QTcF = QT interval duration corrected for heart rate using method of Fridericia; SAE = Serious adverse event; Wk= Week.

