#### **9.1.4.1 Procedures to Manage a Treatment-Emergent Increase in QTcF**

In the event that a subject has a corrected QT interval duration corrected for heart rate using method of Fridericia (QTcF) value exceeding 500 msec, or an increase >60 msec from baseline, the Medical Monitor must be informed. The subject will be asked to return for an unscheduled visit within 24 hours and the ECG will be repeated (confirmed), in triplicate (i.e., three 10-second ECGs in rapid succession within 1 minute). If the repeat measurements confirm that the QTcF is >500 msec or >60 msec from baseline, study treatment will be discontinued and the subject followed until the QTcF value either returns to baseline or until, in the judgment of the Investigator, further evaluation is not clinically indicated.

If study treatment is discontinued, the subject should continue in the study for all remaining scheduled study visits.

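### The follow-up rule for subjects who stop voclosporin but stay in the study is inconsistent, so a site can comply with Section 5.6 without collecting a Week 24 UPCR

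*Combined protocol and SAP*

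**What the plan says.** Three places keep a subject who stops treatment on the full visit schedule:

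- **Synopsis, Procedures.** Subjects who permanently stop before Week 24 "will return for all remaining study visits and assessments, including the 2 Safety Follow-Up visits, unless they have withdrawn consent".
- **Schedule of Events, closing note.** "Subjects who discontinue therapy will be requested to attend their regularly scheduled study visits to the end of the study".
- **Section 9.1.4.1 (QTcF).** "If study treatment is discontinued, the subject should continue in the study for all remaining scheduled study visits".

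Other text on the same subjects is weaker:

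- **Section 5.6** begins by separating the two states: "Discontinuation of study treatment does not necessarily constitute withdrawal from the study". It then says that stoppers, if possible, "should undergo all study assessments up to and including the Week 24 (or Early Termination Visit – Visit 8"). It adds a minimum: "All subjects that discontinue study treatment should attend at least 2 further assessments after the last dose of study drug".
- **Schedule of Events, column heads.** One Visit 8 serves as both end of treatment and early termination. Visits 9 and 10 are tied to Weeks 25 and 26 or, for early stoppers, to discontinuation; Visit 10 reads "Premature Disc. +14 Days".
- **Section 10.3.3** sends a subject taken off treatment for pregnancy to the withdrawal procedures.

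The primary endpoint is remission of proteinuria at Week 24 (Section 13.8.1) in all enrolled subjects (Section 13.3.1). Section 13.4 provides an observed-cases dataset and a last-observation-carried-forward (LOCF) dataset and names neither as primary.

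**The concern.** The Synopsis allows one exception, withdrawn consent. Section 5.6, the body section that governs stopping treatment, allows a second route: an early-termination Visit 8 in place of Week 24, then two post-dose assessments. The Schedule supplies exactly two such visits, at +7 and +14 days. A site that does these three things has met Section 5.6 and the Schedule's column heads without a Week 24 sample. Under the Synopsis the same conduct is a deviation, which also bears on the per-protocol set (Section 13.3.3).

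The reasons for stopping are tied to outcome or tolerability: non-response with transfer to standard of care (Section 7.4.1), a fall in eGFR (Section 7.4.2), QTcF prolongation (Section 9.1.4.1). Week 24 values lost this way would not be missing at random, and the loss could differ by site or cohort. The SAP is to be finalised before database lock (Section 13.1), but it cannot recover urine that was never collected.

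**Working it through.** **1. Which passages conflict.** Sections 4.1, 5.5, 9.2.3 and 9.2.4 also describe Visit 8 plus two follow-up visits, but for subjects who complete or withdraw from the study. They are not part of the conflict. It lies between the Synopsis, the Schedule note and Section 9.1.4.1 on one side, and Section 5.6, the Schedule column heads and Section 10.3.3 on the other.

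**2. What each reading collects.** Take a subject who stops at Week 8.

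- Full follow-up: UPCR at Weeks 12, 18 and 24.
- Close-out: Visit 8 at Week 8, Visit 9 at Week 9, Visit 10 at Week 10. The last UPCR falls 24 − 10 = 14 weeks before the endpoint.
- For a stop at Week 12 the gap is 24 − 14 = 10 weeks; at Week 18 it is 24 − 20 = 4 weeks.

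**3. The plan's own figure.** Section 13.9 gives a 95% Clopper-Pearson interval of 11.9% to 54.3% for 30% of 20. With 6/20, beta quantiles give 11.89% to 54.28%. It reproduces.

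**4. Effect on the remission rate.** Let N be subjects enrolled, d stoppers who are closed out, r completers in remission, w stoppers who would be in remission at a measured Week 24, and s stoppers in remission at the value carried forward.

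- Full follow-up: (r + w)/N
- Close-out, observed cases: r/(N − d)
- Close-out, LOCF: (r + s)/N

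The LOCF shift is (s − w)/N. The observed-cases shift is (d/N) × [r/(N − d) − w/d]. Neither can exceed d/N in size, so each affected subject is worth at most 1/20 = 5 points overall, or 1/10 = 10 points in a cohort of 10.

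**5. Illustration.** Assumptions: N = 20, r = 6, w = 0, and d from 1 to 5. The documents give no stopping rate in FSGS, so d is not an estimate.

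| d | Full follow-up | Observed cases | LOCF, s = 0 | LOCF, s = d (upper extreme) |
|---|---|---|---|---|
| 1 | 6/20 = 30.0% (11.9–54.3) | 6/19 = 31.6% (12.6–56.6) | 30.0% | 7/20 = 35.0% (15.4–59.2) |
| 3 | 6/20 = 30.0% (11.9–54.3) | 6/17 = 35.3% (14.2–61.7) | 30.0% | 9/20 = 45.0% (23.1–68.5) |
| 5 | 6/20 = 30.0% (11.9–54.3) | 6/15 = 40.0% (16.3–67.7) | 30.0% | 11/20 = 55.0% (31.5–76.9) |

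In a cohort of 10 with r = 3, w = 0 and d = 2, the figures are 3/10 = 30.0% with full follow-up, 3/8 = 37.5% for observed cases and 5/10 = 50.0% at the LOCF extreme.

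**6. Nearest figure in the documents.** Section 1.2.4 reports permanent discontinuation for decreased GFR in lupus nephritis of 7.9% at 23.7 mg and 5.7% at 39.5 mg. Applied to 20 subjects, that is 0.079 × 20 = 1.6 and 0.057 × 20 = 1.1, so one or two. It is a different disease and only one reason for stopping.

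**The case against.** The strongest reply is that Section 5.6 is not a rival rule. It separates stopping drug from leaving the study, and its main clause asks for every assessment through Week 24, as the Synopsis does. Early termination is half of Visit 8's own label, so the bracket may be meant for those who later leave. Two assessments is a minimum, not an instruction to stop there. The +7 and +14 day visits can sit alongside the remaining scheduled visits, which fits the endpoints in Section 13.8.2 that run from the last on-treatment visit to Visit 10.

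Much of this stands. A reader might infer that a site following Section 5.6 and the Schedule has no reason to bring the subject back for Week 24. The documents do not support that: the Schedule's own note requests attendance to the end of the study. What remains is that the bracket in Section 5.6 is not limited to subjects who leave, and the combined reading is nowhere written down.

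On size, a reader might infer a bias of 10 points or more. That rests on assumed inputs. Subjects who stop for non-response are unlikely to be in remission at the stop, and with s = w = 0 the LOCF shift is zero. If some remit later on standard of care, w exceeds s and LOCF understates the Week 24 rate. It can also be argued that the ITT set calls for a denominator of all enrolled; with missing values counted as not in remission, the illustration returns to 6/20. But Section 13.4 does define an observed-cases dataset, and no rule counts a missing Week 24 as non-remission.

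The analyses are also descriptive and hypothesis-generating (Sections 13.2 and 13.9). That limits the consequence but does not remove it.

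**Conclusion.** The inconsistency holds and should be corrected. The text leans towards full follow-up, but Section 5.6 and the Schedule's column heads can be satisfied without a Week 24 UPCR, and the timing of Visits 8 to 10 for a stopper who stays in is not stated. Because stopping is related to outcome, primary-endpoint data lost this way would be informative.

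Under LOCF a stopper with any post-baseline value still has a Week 24 entry. The question there is which value it is: one from the stop, an early off-drug one from Visit 9 or 10, or a measured Week 24 one.

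The size is unknown. It is bounded at 5 points per affected subject among 20 and 10 points in a cohort of 10. The direction is not fixed, and the shift may be zero. The tabulated shifts depend on assumed numbers of stoppers and their assumed remission status. The separate gap that neither dataset in Section 13.4 is primary adds to the uncertainty, and the fix below does not close it.

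**What to change.** Reconcile Section 5.6 and the Schedule of Events to the Synopsis:

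- **Section 5.6.** State that a subject who stops drug without withdrawing consent attends every remaining scheduled visit, including calendar Week 24 with a first-morning-void UPCR. Limit the early-termination alternative to subjects who leave the study.
- **At the stop.** Keep the end-of-treatment assessments there. Visit 8 carries the only scheduled post-baseline ECG, so moving it wholesale to Week 24 would lose the assessment at the stop. Give the stopper's Week 24 visit its own label.
- **After the stop.** Keep the +7 and +14 day visits in addition to the remaining visits, and keep the +14 day visit as Visit 10. If Visit 10 moved to Week 26, the off-drug change in Section 13.8.2 for a Week 8 stopper would span 26 − 8 = 18 weeks instead of 2. State whether anything is due at Weeks 25 and 26. Also state whether adverse events are still recorded after the +14 day visit, since Section 10.3.1 ends reporting at Visit 10.
- **Two-assessment minimum.** Keep it only as a floor for those who cannot attend everything.

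The cost is a wording amendment and a few extra visits for the few stoppers. The visits are already called for in one part of the protocol or another. No dose or stopping criterion changes.

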### **5.6.1 Discontinuation of Study Treatment Due to an Adverse Event**

Subjects may be permanently discontinued from study treatment because of the appearance of an unacceptable AE. It is vital to obtain follow-up data on any subject discontinued because of an AE. In any case, every effort must be made to evaluate protocol-specified safety follow-up procedures (see [Section 10.3, Reporting Procedure for AEs, SAEs, and Pregnancy](#)). If a subject

is discontinued due to an AE, the event should be followed by the Investigator through contact with the subject until resolution or stabilization has occurred. All AEs should be followed until resolution, stabilization or the subject is lost to follow-up and cannot be contacted.

## **6. RANDOMIZATION, BLINDING AND UNBLINDING PROCEDURES**

Not applicable.

## 7. STUDY TREATMENTS

### 7.1 Dosage Forms/Formulation

All study treatment to be used in this study will be manufactured in accordance with current Good Manufacturing Practice (GMP). Study treatment will be supplied by Aurinia Pharmaceuticals Inc. (Aurinia).

#### 7.1.1 Voclosporin – Study Treatment

Company Code: [REDACTED]

Chemical Name: [REDACTED]

Empirical Formula: [REDACTED]

Generic Name: Voclosporin

Dosage Form: Softgel capsules

Strength: 7.9 mg of voclosporin per softgel capsule

Manufacturer: [REDACTED]

#### 7.1.2 Dosing Guidelines

##### 7.1.2.1 Voclosporin

Voclosporin will be taken BID with water on an empty stomach as close to a 12-hour schedule as possible, and with a minimum of 8 hours between doses. If the subject misses a dose of study treatment by less than 4 hours from the anticipated dosing time, the missed dose will be taken immediately. The next dose will be taken at the originally scheduled time. If a missed dose of study treatment is greater than 4 hours from the expected dosing time, the subject will skip the dose and take the next dose at the originally scheduled time. The variation in dosing will be recorded in the eCRFs. The dose/doses of study treatment may be held at the discretion of the Investigator. Subjects must avoid consumption of grapefruit or grapefruit-containing juice (e.g., pomelo) for the duration of their participation in the study.

The dosing of voclosporin for Cohort 1 will be as follows:

- Week 1: 1 capsule (7.9 mg) orally (PO), BID
- Week 2: 2 capsules (15.8 mg) PO, BID

- Weeks 3 to 24: 3 capsules (23.7 mg) PO, BID

Evaluable safety and tolerability data from 12 weeks of treatment in the first 5-6 subjects from Cohort 1 are required in order to make the decision to escalate to a higher dose level for Cohort 2. The selected dose may be higher or lower than 23.7 mg BID. The maximum dose possible for Cohort 2 will be 39.5 mg (5 capsules) BID. Should this dose be selected the following dosing regimen will be followed:

- Week 1: 1 capsule (7.9 mg) PO, BID
- Week 2: 2 capsules (15.8 mg) PO, BID
- Week 3: 3 capsules (23.7 mg) PO, BID
- Weeks 4 to 24: 5 capsules (39.5 mg) PO, BID

All subjects will be contacted by telephone at the end of Week 1 and Week 2 (and Week 3, if applicable) to be reminded to increase their dose.

If the 39.5 mg dose is selected for Cohort 2, subjects still receiving treatment in Cohort 1 may have their dose increased to 39.5 mg BID after Week 8 per Investigator judgement and following discussion with the Medical Monitor.

All unused study treatment (and any empty containers) dispensed to the subject will be returned at each study visit for capsule counts to check compliance. The Investigator will count the returned study treatment, and this information will be used to assess subject compliance.

This study treatment count must be documented in the eCRF and source documentation.

#### **7.1.2.2 Corticosteroids**

Subjects entering the study with corticosteroids should have their steroid dose gradually titrated down until they achieve a daily dose of <10 mg/day prednisone by Week 12. The timing of the titration is at the discretion of the investigator, with a reduction of 5 mg/day every 2 weeks recommended. If clinically indicated, steroid tapering may start during the stability assessment period. A dose level may be maintained for up to 4 weeks or increased per investigator judgement following discussion with the Medical Monitor. Refer to [Appendix 4](#) for a conversion table of various formulations of steroids.

Corticosteroid treatment must be documented in the eCRF and source documentation.

When clinically indicated, subjects are allowed to be completely titrated off oral corticosteroids.

Corticosteroids should not be re-started in a patient whose dose has been reduced to zero, or initiated during the study in treatment-naïve patients, without prior discussion with the Medical Monitor.

## **7.2 Package and Labeling**

All study treatments provided by Aurinia will be packaged and labeled for Aurinia by appropriately qualified vendors according to all applicable local and country regulatory requirements. All packaging and labeling operations will be performed according to GMP and Good Clinical Practice (GCP).

Study-treatment wallets provided to sites and to subjects will be labeled in the appropriate local language, according to local regulatory requirements.

Wallet label information will be appropriately documented in the Drug Accountability Form after the container has been dispensed to the subject.

## **7.3 Site Supply, Storage, Accountability**

### **7.3.1 Site Supply**

Once a site has been approved for study initiation, the site will be supplied with an initial stock of study treatment. The need for study treatment resupply will be assessed on a regular basis taking into account the number of subjects enrolled at the site.

### **7.3.2 Storage**

Voclosporin softgel capsules will be supplied in cartons containing 168 capsules in 4 wallets of 42 capsules each.

The Investigator must ensure the availability of proper storage conditions. All study treatment supplies provided for this study will be stored in a secure area with restricted access at the study site. The capsules must be stored at a controlled room temperature between 15 and 30°C (59-86°F). The Investigator must document and inform the Site Monitor about temperature deviations outside the acceptable range. Subjects will be instructed to store the study treatment at room temperature between 15 and 30°C (59-86°F).

Each site should have a thermometer that records minimum and maximum temperatures daily. Maintenance of a temperature log is mandatory. The log should be updated by site personnel during normal working hours. This log must be available for review by the Site Monitor during on-site monitoring visits.

### **7.3.3 Accountability**

The Investigator at each site is responsible for study treatment supplies. The Investigator will ensure that adequate records of the receipt, dispensing, and return of the study treatment are

kept and that the study treatment is used only for subjects enrolled in the study. All data regarding the study treatment must be recorded on the relevant forms provided.

Each study site will maintain a drug inventory/dispensing record for all drugs dispensed and returned. At the end of the study, one copy of the drug inventory/dispensing record should be sent to Aurinia for the central study file. The original will be kept in the site files.

After completion of the study, or if it is prematurely terminated, all unused materials will be returned to Aurinia. The decision to destroy study treatment at a site must be made by Aurinia. If the study treatment is destroyed at a site, the Investigator must receive Aurinia's approval of the process and forward the certificate of destruction to Aurinia.

## **7.4 Voclosporin Dose Modification**

### **7.4.1 Discontinuation of Study Therapy Due to Non-response**

During the treatment period, any case where the subject experiences a worsening of proteinuria, or no improvement in proteinuria from baseline, once the highest permitted dose of study drug has been achieved, should be discussed with the Medical Monitor. Subjects may be allowed to add treatment with corticosteroids (IV or oral) while continuing with study drug, or may be discontinued from study treatment and transitioned to standard of care treatment.

If the dose level of 39.5 mg BID is determined for Cohort 2, any subject still on treatment in Cohort 1 who has completed 8 weeks of treatment and shown no meaningful improvement in proteinuria may have their dose increased to 39.5 mg BID per Investigator judgement and following discussion with the Medical Monitor.

